## 9. Safety

### 9.1. Definitions of Adverse Events and Adverse Drug Reactions

#### 9.1.1. Adverse Event

An adverse event (AE) is any untoward medical occurrence in a clinical trial participant administered a study drug (i.e., IMP or placebo), even if the event is not considered to be caused by study drug. The adverse event may be, but is not restricted, to any new illness, worsening of a sign or symptom of COVID-19, or deterioration of a pre-existing medical condition. Abnormal laboratory results and results of physical examinations after the screening examination constitute Adverse Events to be reported and graded according to the CTCAE Grading table (v 5.0) if they are considered as clinically significant and/or require treatment.

#### Pregnancy

For reasons of drug safety, the occurrence of a pregnancy during the conduct of this trial is to be regarded as an AE. For details of special reporting requirements for pregnancy, see section 9.3.2.

#### Adverse Events of Special Interest

Infusion-related reactions presenting as hypersensitivity/allergic reaction, anaphylaxis, or cytokine release syndrome; as well as inhalation-related reactions presenting as allergic reaction (e.g., bronchospasm that may manifest with wheezing and/or respiratory distress) are designated as Adverse Events of Special Interest. For details of reporting requirements, see section 9.3.1.

#### 9.1.2. Adverse Drug Reaction

All adverse events judged by either the investigator or the sponsor as having a reasonable suspected causal relationship to the study drug product qualify as adverse drug reactions (ADR).

### **9.1.3. Serious Adverse Events and Serious Adverse Reactions**

A serious adverse event (SAE) or serious adverse drug reaction (SAR) is any adverse event or adverse drug reaction that

- results in death, and/or
- is life-threatening at the time of the event, and/or
- requires inpatient hospitalization or prolongation of existing hospitalization, and/or
- results in persistent or significant disability/incapacity, and/or
- is a congenital anomaly/birth defect, and/or
- is any other medically important event in the opinion of the investigator (e.g., an event that may jeopardize the trial subject or may require intervention to prevent one of the outcomes listed above)

Inpatient hospitalization is defined as any stay in a hospital that includes at least one night (midnight to 6 am).

Admission to hospital that was planned before the first study drug administration will not be considered as SAE but must be documented in the trial subject's medical records and CRF.

Inpatient hospitalization for the purpose of IMP administration is not considered as SAE, but must be documented in a proper manner in the trial subject's medical record and CRF. Prolongation of hospitalization must be documented and reported as SAE.

### **9.1.4. Unexpected Adverse Drug Reaction**

An unexpected adverse drug reaction is an ADR that is not consistent with the potential ADRs listed in the Investigator's Brochure in severity, nature and/or outcome.

### **9.1.5. Suspected Unexpected Serious Adverse Reactions**

A suspected unexpected serious adverse reaction (SUSAR) is a serious adverse event (SAE) the nature or severity of which is not consistent with the potential ADRs listed in the Investigator's Brochure, and that has at least a possible causal relationship to the study drug.

### **9.1.6. Dose-Limiting Toxicities**

A dose-limiting toxicity (DLT) will be defined as any grade 3 or higher adverse event during the dose escalation phase of the trial (**Groups 1A-1C, 2A-2C**) that is assessed by the trial investigators to be related to DZIF-10c. For details on reporting requirements see section 9.3.1.

## 9.2. Documentation and Follow-Up of Adverse Events

### 9.2.1. Documentation of Adverse Events and Adverse Drug Reactions

The occurrence of (S)AEs and ADRs will be documented starting with the provision of informed consent and until the termination of the clinical trial for the individual participant using the applicable case report form (CRF).

All adverse events, regardless of whether a causal relationship between the AE and study drug is suspected, will be followed-up until the associated symptoms have subsided, abnormal laboratory results have returned to pre-event levels, or the study has been completed or terminated for the individual participant.

Persistent AEs that do not resolve between individual visits will be recorded once. The initial severity will be documented at the time the event is first reported, and the highest severity will be documented should the persistent AE become more severe.

Should an AE become serious within the reporting period, it should be reported to the sponsor immediately (i.e., no more than 24 hours after learning that the event became serious) by using the trial-specific SAE form. Additionally, as soon as a documented Adverse Event becomes serious, the SAE information should be amended on the AE eCRF page by providing the date that the event became serious as onset date of the SAE and completing all data fields related to serious adverse event.

Documentation of AEs includes

- Description of AE
- Date and time of onset and resolution
- Grading/Severity
- Relationship to study drug
- Seriousness
- Effect on the trial drug administration schedule
- Need for treatment and action taken
- Outcome
- Written summary / narrative (for SAEs, AESIs, and DLTs)

Pre-existing diseases (i.e., medical conditions starting before study drug administration) are not documented as AEs but as medical history. However, worsening of pre-existing diseases will be documented as AEs.

### 9.2.2. Severity of Adverse Events

The CTCAE (Common Terminology Criteria for Adverse Events) grading table (v5.0) will be used by trial investigators to classify adverse events. It comprises the following categories:

- **Grade 1: Mild.**  
Asymptomatic or mild symptoms; clinical or diagnostic observations only; intervention not indicated.
- **Grade 2: Moderate.**  
Minimal, local or noninvasive intervention indicated; limiting age-appropriate instrumental activities of daily living\* (ADL).
- **Grade 3: Severe or medically significant but not immediately life-threatening.**  
Hospitalization or prolongation of hospitalization indicated; disabling; limiting self-care ADL\*\*.
- **Grade 4: Life-threatening consequences.**  
Urgent intervention indicated.
- **Grade 5: Death related to AE.**

\*Instrumental ADL refer to preparing meals, shopping for groceries or clothes, using the telephone, managing money, etc.

\*\*Self-care ADL refer to bathing, dressing and undressing, feeding self, using the toilet, taking medications, and not bedridden.

### 9.2.3. Causality Assessment of Adverse Events

Every AE will be assessed by a trial investigator for potential causal relationship to the study drug. This assessment will include consideration of the nature and type of reaction, the temporal relationship with the study drug, the clinical status of the trial participant, concomitant medication and other relevant clinical factors. If the event is considered to be a consequence of lack of study drug efficacy or to be a symptom or sign of the underlying disorder, no causal relationship to the study drug will be assumed.

AEs/SAEs will be assessed according to the causality determinations of CIOMS VI-Group (Council for International Organizations of Medical Sciences) as follows:

- Related: There is a reasonable possibility that the AE is related to the IMP.
- Not related: There is not a reasonable possibility that the AE is related to the IMP.

Events for which no causal relationship to the IMP is given or which are classified as "not assessable" will be regarded as related until enough information is provided to allow a proper assessment of the causal relationship.

The causality assessment given by the investigator should not be downgraded by the Sponsor. If the Sponsor disagrees with the Investigator's causality assessment, the more critical assessment is to be used for further processing of the case and the opinion of both, the Investigator and the Sponsor, will be provided the report narrative.

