Ad-hoc SMC meetings will be conducted prior to enrolment into **Groups 1B, 1C, 2B, 2C, and 2D** to provide recommendations on proceeding with the dose escalation scheme. A review of the safety data from the intravenous doses administered in the Uni-Koeln-4288 trial will be conducted prior to inclusion of the intravenous dose in **Group 2D** to decide on whether to include intravenous infusion of DZIF-10c and at which dose. A lower dose than the targeted 40 mg/kg dose will be used in case that a lower maximum tolerated dose for the intravenous infusion of DZIF-10c has been determined in the trial Uni-Koeln-4288.

Additional SMC meetings may be scheduled on an as-needed-basis if deemed necessary by the members of the SMC, the Sponsor, or the Principal Investigators.

On an interim basis, the SMC will also be asked to review the following data:

- Any grade 3 or higher Adverse Events (AEs) that are deemed to be related to DZIF-10c by the Investigators.
  - These events will also be assessed as potential late-occurring dose-limiting toxicities (i.e., after dose-escalation has proceeded and/or been completed) to evaluate whether a change to study dosing is warranted.
  - In case of grade 3 or higher AEs deemed related to DZIF-10c occurring in two or more participants, administration of DZIF-10c will be halted until a SMC review has been completed to provide recommendations regarding subsequent study enrolment.
- Serious Adverse Events (SAEs) that are deemed related to DZIF-10c by the Principal Investigator or designee. Such events need to be reported to the SMC within one business day of the Sponsor becoming aware of the event.
  - No additional administration of DZIF-10c will occur after an SAE deemed related to DZIF-10c until an SMC review has been completed to provide recommendations regarding subsequent study enrolment.
  - In case of life-threatening, fatal, or permanently disabling SAEs deemed related to DZIF-10c, no further administration of DZIF-10c will occur until a consensus plan has been approved by the SMC, Investigators, the Sponsor, the principal ethics committee, and the PEI.

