#### Dose-Limiting Toxicities

A dose-limiting toxicity (DLT) for this trial will be defined as any grade 3 or higher adverse event during the dose escalation phase that the investigators determine to be related to DZIF-10c.

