### 4.2.1. Potential Risks and Strategies for Risk Mitigation

#### Antibody-dependent enhancement

Antibody-dependent enhancement (ADE) of disease or infection is a potential concern of all antibody-mediated strategies, including vaccination, against infectious pathogens. It is best, albeit rarely, documented for severe courses of disease after dengue virus (re)-infection in the presence of low neutralizing antibody titers. However, dengue virus replicates in Fc receptor-expressing cells (e.g., monocytes and dendritic cells). Thus, Fc-mediated cellular uptake of antibody-bound virus may result in increased infection, viral propagation, and enhanced disease for dengue virus infection. Antibody-mediated worsening of clinical symptoms can in principle also result from an overstimulation of the immune response, e.g., by immune complex-mediated activation of the complement system. However, monoclonal antibodies targeting the respiratory viral pathogens RSV and influenza virus have been administered for treatment and prevention of disease without signs of increased disease. Importantly, the administration of convalescent plasma with varying levels of neutralizing and non-

neutralizing antibodies to tens of thousands of individuals has not been reported to be associated with an increased severity of disease. Similarly, antibody-dependent enhancement of disease was not reported in a phase II clinical trial of a SARS-CoV-2-neutralizing monoclonal antibody administered to recently infected outpatients. In addition, neither neutralizing nor sub-neutralizing concentrations of DZIF-10c were associated with increased infection or replication in CD14-derived human macrophages co-cultured with authentic SARS-CoV-2- *in vitro*.

*Risk mitigation strategy:* Infusion of DZIF-10c to SARS-CoV-2-infected individuals will be initiated open-label and staggered by at least one day during the dose escalation phase of the trial (i.e., a maximum of one participant to be enrolled per dose group per day, **Groups 2A-2C**). Participants will be closely followed for clinical signs of disease enhancement (e.g., respiratory distress, reduced SpO2).

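### Suspected antibody-dependent enhancement may escape the automatic safety rules, because section 9.2.3 steers COVID-19-like worsening towards not related and those rules need a related event

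*Protocol*

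**What the plan says.** Protocol 4.2.1 puts antibody-dependent enhancement first among the risks. Its mitigation is open-label, staggered dosing in Groups 2A-2C plus observation: "Participants will be closely followed for clinical signs of disease enhancement", with respiratory distress and reduced SpO2 as examples. No threshold or reporting trigger is attached.

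Protocol 9.2.3 asks the investigator to judge every AE as related or not. The standard for related is "There is a reasonable possibility that the AE is related to the IMP". One class of event is then settled by rule: "If the event is considered to be a consequence of lack of study drug efficacy" is the first condition, and the sentence continues "or to be a symptom or sign of the underlying disorder, no causal relationship to the study drug will be assumed". The same section says that events with no causality given, or classed as not assessable, "will be regarded as related until enough information is provided to allow a proper assessment of the causal relationship". Where sponsor and investigator disagree, "the more critical assessment is to be used for further processing of the case".

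The rules that act automatically are tied to relatedness:
- A DLT (4.1.1, repeated in 9.1.6) is "any grade 3 or higher adverse event during the dose escalation phase that the investigators determine to be related to DZIF-10c".
- In 3.4, the interim items sent to the SMC are grade 3 or higher AEs deemed related by the investigators, and "Serious Adverse Events (SAEs) that are deemed related to DZIF-10c by the Principal Investigator or designee".
- The dosing pauses in 3.4 follow related grade 3 or higher AEs in two or more participants, or a related SAE. Stricter conditions for resuming apply if a related SAE is life-threatening, fatal or permanently disabling.

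The AESI list (5.2.1, 9.1.1) covers infusion-related and inhalation-related reactions only.

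**The concern.** In an infected participant, enhancement and ordinary progression of COVID-19 look alike at the bedside. An investigator who sees worsening breathlessness or falling saturation a few days after dosing has a ready explanation in the infection, and 9.2.3 turns that explanation into a finding of no causal relationship. Section 5.2.6 adds to the pull: investigators must also judge whether each hospitalization is related to COVID-19, and a hospitalization caused by enhancement would be.

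An event classified that way is not a DLT, does not count towards a pause and is not an item that 3.4 requires to be sent to the SMC between its scheduled meetings. At stake is whether the harm that the protocol itself names for infected recipients has a dependable route to the safety body, above all in Group 2D, which includes the first combined inhaled and intravenous use.

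**Working it through.** The documents state no figure on this point, so the check is first of the text and then an illustration on assumed rates.

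**Step 1: does the causality rule reach enhancement?** Section 1.1 describes severe COVID-19 by lower respiratory signs such as dyspnea and respiratory failure. Section 4.2.1 gives respiratory distress and reduced SpO2 as signs of enhancement. The two overlap. Section 9.2.3 has no exception for suspected enhancement, so it steers such events towards not related. It does so only once the investigator considers the event a sign of the disease. The classification is therefore likely, not fixed.

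**Step 2: what does not depend on relatedness?** SMC meetings are required before Groups 1B, 1C, 2B, 2C and 2D (3.4). For escalation, the SMC reviews interim safety data after the day 7 visits (4.1.1), with no restriction to related events. In the escalation groups, worsening should thus reach the SMC before the next step, whatever its coding.

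**Step 3: what is left in Group 2D?** DLTs are confined to Groups 1A-1C and 2A-2C (9.1.6). Investigators are blinded (5.9.6). The last meeting named in 3.4 comes before Group 2D enrols. The unblinded analysis follows the last participant's day 7 visit (Protocol 5.9.6.1 and 8.1; SAP 9.1.2.1), when all 60 have been dosed. SAP 7.4.2 repeats the summary of DLT-criteria events without regard to relatedness, but as descriptive reporting.

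**Step 4: is the sponsor's re-assessment a full backstop?** Section 9.3.3 has sponsor assessors re-judge the causality of SAEs only. The DLT and grade 3 rules cite the investigators' judgement, and the SAE item cites the Principal Investigator or designee. The protocol does not say whether a sponsor upgrade counts for those rules.

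**Step 5: illustration.** Let p be the true rate of drug-caused grade 3 or higher worsening and q the chance that such a case is called related. Both are assumptions. The rate that the rules can see is r = p × q.

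- *3+3 rule.* A group proceeds with probability (1−r)³ + 3r(1−r)²(1−r)³. For p = 20% and q = 1, r = 0.20: 0.512 + 3 × 0.20 × 0.64 × 0.512 = 0.709. The chance of at least one halt across Groups 2A-2C is 1 − 0.709³ = 64%.
- *Two-participant pause in Group 2D.* There are 20 + 20 = 40 DZIF-10c recipients. P(at least 2) = 1 − (1−r)⁴⁰ − 40r(1−r)³⁹. For p = 10% and q = 1, r = 0.10: 1 − 0.015 − 0.066 = 92%.

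| Share called related (q) | Halt in 2A-2C, p = 20% | Halt in 2A-2C, p = 33% | At least 2 related among 40 in 2D, p = 10% |
|---|---|---|---|
| 0 | 0% | 0% | 0% |
| 0.25 | 8% | 19% | 26% |
| 0.5 | 26% | 52% | 60% |
| 1 | 64% | 92% | 92% |

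The last column understates the response to serious cases, because a single related SAE already pauses dosing. If every case were also an SAE, the chance of at least one related SAE among 40 at p = 10% would be 1 − (1−r)⁴⁰: 64% at q = 0.25 (r = 0.025), 87% at q = 0.5 (r = 0.05) and 99% at q = 1 (r = 0.10). At q = 0 it is still zero.

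**The case against.** A reader might infer that 9.2.3 declares any worsening of COVID-19 unrelated, that enhancement can never trigger a safety rule, and that the trial cannot detect it. The documents support none of these.

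- The rule is conditional on the investigator's view. Every AE is assessed individually against a reasonable-possibility standard, and nothing stops an investigator from calling suspected enhancement related.
- Not-assessable events default to related, sponsor assessors re-judge SAEs, and the more critical view governs further processing.
- The SMC meetings before escalation steps and before Group 2D need no related event. Section 3.4 also has the SMC review both trials' data as they progress, with details in a charter that is not among the documents, and allows extra meetings at need.
- COVID-19 worsening is an AE (9.1.1). All SAEs reach the sponsor within 24 hours (9.3.1). Vital signs including SpO2 and the WHO scale are scheduled at every visit (Appendix II B). AEs and COVID-19-related hospitalizations are summarised by arm whatever the causality.
- The protocol describes the infected population as at relatively low risk of progression (4.3), so high assumed rates of worsening should not be read as predictions.

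All of this stands, and it removes the absolute claims. It does not close the gap. Reporting tables do not pause anything. Ad-hoc meetings need someone to suspect a signal, and blinded sites cannot see an imbalance between arms. The undertaking to review data as they progress names no dates or content for Group 2D, and a charter that supplies them may exist. The remaining routes depend on judgement exactly where the causality wording pulls the other way.

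**Conclusion.** The concern holds in limited form. Section 9.2.3 lowers the chance that enhancement is called related, and every automatic DLT, pause and event-driven SMC rule depends on that call. Enhancement may therefore escape those rules without being excluded from them. The weakness is modest in Groups 2A-2C, where the SMC sees interim safety data before each step. It is greatest in Group 2D.

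The size cannot be taken from the documents. In the illustration, the Group 2D two-participant pause falls from 92% to between 26% and 60% when a quarter to a half of cases are called related. The 3+3 halt across 2A-2C, at p = 20%, falls from 64% to between 8% and 26%. These figures assume the rates p and q, independent cases, the same rates in all groups and onset within the 3+3 window. They leave out background progression. The textual finding does not rest on them; it does rest on the protocol alone, since the SMC charter could narrow the Group 2D gap.

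**What to change.** 1. Reconcile 9.2.3 with 4.2.1, 3.4 and 9.1.6, so that a site can tell how suspected disease enhancement is to be classified. State whether a sponsor upgrade of causality counts for the DLT and pause rules. While doing so, reword the sentence in 9.2.3 on events for which no causal relationship is given: it seems to mean a missing assessment, but can be read against the rule just before it.
2. In the 3.4 list of interim data for the SMC, add listings of all SAEs and all grade 3 or higher respiratory or COVID-19-worsening AEs in infected participants, regardless of causality. For Group 2D, these can go by arm to the SMC only, through the statistics institute that prepares the randomization and performs the unblinding. The placebo arm is what lets the SMC set such events against background progression.

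This changes what the SMC is shown. What the classification should be, and any halting or dosing consequence, stay with the sponsor and the SMC. The cost is protocol wording, a few extra listings and some SMC e-mail reviews, which 3.4 already allows. Sites and sponsor stay blinded. If the charter already provides for such listings in Group 2D, a cross-reference in 3.4 would do for the second item.

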### **9.3. Reporting of Serious Adverse Events, Adverse Events of Special Interest, Dose-Limiting Toxicities, Pregnancy and Changes in Risk-Benefit Assessment**

Every SAE that occurs from the provision of informed consent to participate in the trial until the trial participant's last study visit must be documented on the appropriate CRF and in addition be reported on a SAE form to the sponsor. In the interest of participants' safety, follow-up for up to 30 days after the individual participant's study termination is required for SAEs that are not sufficiently resolved at the participant's final trial visit.

Adverse Events of Special Interest (AESIs) and Dose-Limiting Toxicities (DLTs) should be reported to the sponsor within 24 h of the site becoming aware of the event.

Pregnancies must be documented on a separate pregnancy form and reported to the sponsor within the defined periods (see Section 9.3.2.).

An Investigator Handout providing detailed information of reporting procedures will be provided to the trial sites.

#### **9.3.1. SAE, AESI and DLT Reporting**

All serious adverse events (SAEs) occurring between the provision of informed consent to participant in the trial and the participant's last trial visit must be reported by the local trial investigator to the sponsor without delay and at the latest within 24 hours of becoming aware of the SAE.

To this end, the provided SAE report forms must be completed and submitted by fax or E-Mail to the Clinical Trials Center Cologne (CTCC, ZKS Köln) to which the sponsor has delegated the SAE management procedures:

**SAE Dedicated Facsimile:** [REDACTED]

**SAE Reporting E-Mail:** [REDACTED]

Similarly, AESIs should be reported on AESI report forms and must be completed and submitted by fax or E-Mail to the Clinical Trials Center Cologne (CTCC, ZKS Köln) within 24 h of the site becoming aware of the event.

Finally, DLTs occurring during the dose-escalation phase of the trial (**Groups 1A-1C, Groups 2A-2C**) must be reported by submitting the AE/DLT report form by fax or E-Mail to the Clinical Trials Center Cologne (CTCC, ZKS Köln) within 24 h of the site becoming aware of the event.

